### 11.3 Baseline Lung Allograft Dysfunction

Baseline Lung Allograft Dysfunction (BLAD) at baseline (Yes, No) will be reported in the demographic table. BLAD patients are defined as patients with baseline FEV1/predicted FEV1\*100 <80% [10]. The following formula for the calculation of predicted FEV1 will be used:

Predicted FEV1 =  $b_0 + b_1 * age + b_2 * age^2 + b_3 * height^2$ 

where the coefficients of the regression are reported in Table 3.

Table 3: Coefficients for FEV1 Prediction

I ubic J.	svejjicienis joi TEV II realciton				
Sex	Ethnicity	Intercept (b 0 )	Age (b₁)	Age  (b 2 )	Ht (cm)  (b 3 )
Male	Caucasian < 20 yr of age	-0.7453	-0.04106	0.004477	0.00014098
Male	Caucasian ≥ 20 yr of age	0.5536	-0.01303	-0.000172	0.00014098
Male	African-American < 20 yr of age	-0.7048	-0.05711	0.004316	0.00013194
Male	African-American ≥ 20 yr of age	0.3411	-0.02309	0	0.00013194
Male	Mexican-American < 20 yr of age	-0.8218	-0.04248	0.004291	0.00015104
Male	Mexican-American ≥ 20 yr of age	0.6306	-0.02928	0	0.00015104
Female	Caucasian < 18 yr of age	-0.8710	0.06537	0	0.00011496
Female	Caucasian ≥ 18 yr of age	0.4333	-0.00361	-0.000194	0.00011496
Female	African-American < 18 yr of age	-0.9630	0.05799	0	0.00010846
Female	African-American ≥ 18 yr of age	0.3433	-0.01283	-0.000097	0.00010846
Female	Mexican-American < 18 yr of age	-0.9641	0.06490	0	0.00012154
Female	Mexican-American ≥ 18 yr of age	0.4529	-0.01178	-0.000113	0.00012154

Due to eCRF study design, ethnicity has not been recorded as required for Table 3, and as a result, the race field as recorded in the eCRF will be used for mapping as detailed below in Table 4.

Table 4: eCRF Race Classification

eCRF Term	Remapping			
White	Caucasian			
Black or African American	African-American			
Asian	0.88% reduction will be used versus the Caucasian			
Other	check "other, specify" to see additional race info.			
	
 
If patients are defined as "white" or "black/African", please use the corresponding classification.
 
If patients are defined as "latinos", then use "Mexican-American".
 
If patient is defined as "Arabian" then treat as the Asian category with the 0.88% reduction used versus the Caucasian.
 
			
	Otherwise consider them as "unknown"			

Final Version 5.0 Page 34 of 76

For Asian or Other field with Arabian ethnicity, the calculation will be performed using the Caucasian coefficients of Table 3 (considering the corresponding sex, age, and height values) and then applying a correction factor of 0.88 [12]. For example, in case of an Asian male patient older than 20 years, the calculation will be:

Predicted FEV1 = 0.88 \* (0.5536 - 0.01303 \* age - 0.000172 \* age + 0.00014098 \* height).

In case of other races (American Indian or Alaskan, Native, Native Hawaiian or Other, Pacific Islander), unknown, or unspecified ethnicities (including "multiracial", "multicultural", "mixed", etc.), parameters calculated as average of the Caucasian, African-American, and Mexican-American parameters will be used, according to Table 4:

Table 4: 0	Coefficients for	r FEV 1 Predict	tion for oth	er/unspecified	ethnicities.
Sex	Age class	Intercept	Age	Age 	Ht (cm) 
	Age class	$(b_0)$	(b₁)	(b 2 )	(b₃)

		(b 0 )	(b 1 )	(b 2 )	(b 3 )
Male	< 20 yr of age	-0,7573	-0,04688	0,004361333	0,000141
Male	≥ 20 yr of age	0,508433	-0,0218	-0,0000573	0,000141
Female	< 18 yr of age	-0,9327	0,062753	0	0,000115
Female	≥ 18 yr of age	0,409833	-0,00941	-0,000134667	0,000115

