#### **Eligibility Criteria:**

#### Inclusion Criteria:

[figure not shown]
- 1. Adult patients  $\geq$  18 years who received a double lung transplant at least 12 months prior to Screening.
- 2. Patients with BOS diagnosis defined as CLAD-BOS phenotype with:
  - a) Screening FEV1 between 85-51% of personal best FEV1 value post-transplant.

OR

- b) Screening FEV1 >85% of personal best FEV1 associated with EITHER a  $\geq$  200 mL decrease in FEV1 in the previous 12 months OR according to medical history showing BOS progression.
- 3. Diagnosis of CLAD-BOS must be made at least 12 months after lung transplantation and
  - a) within 12 months prior to the screening visit OR
  - b) more than 12 months from screening and patient must have shown a decline in FEV1 ≥ 200ml in the previous 12 months before screening, which is not due to acute infection or acute organ rejection
- 4. Patients in whom the diagnosis of BOS has been confirmed by the elimination of other possible causes of obstructive or restrictive lung disease (CLAD RAS phenotype, see Protocol Specific Definitions).
- 5. Patients should be maintenance regimen on a immunosuppressive agents including tacrolimus, a second agent such as but not limited to MMF or azathioprine, and a systemic corticosteroid such as prednisone as third agent. The regimen must be stable within 4 weeks prior to randomization with respect to the therapeutic agents. In case a patient is also receiving concomitant azithromycin for prophylaxis or treatment of BOS, in addition to the previously described immunosuppressive regimen, azithromycin must be on a stable regimen for at least 4-weeks prior to randomization.
- 6. Patients capable of understanding the purposes and risks of the clinical trial, who have given written informed consent and agree to comply with the clinical trial requirements/visit schedules, and who are capable of aerosol inhalation. Patients must consent to retrieve prespecified data from the historic

[figure not shown]
Sponsor:

Zambon SpA

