In its most common presentation, BO is characterized by the pathophysiological features of respiratory obstruction. The major findings on spirometry are a reduced forced expiratory volume in 1 second (FEV1), a normal, or slightly decreased forced vital capacity (FVC), and a reduced ratio of FEV1 to FVC, with poor response to inhaled bronchodilators. Lung volumes indicate air trapping, with a normal total lung capacity and high residual volume. However, a subset of patients present with a restrictive pattern characterized by a low FVC and a normal ratio, or a mixed pattern of obstruction and restriction [Barker 2014]. BOS is often a diagnosis of exclusion

and other causes of allograft dysfunction, including restrictive allograft syndrome (RAS), acute rejection, and acute infection, need to be excluded before the diagnosis of BOS is made [Glanville 2019].

The 2002 BOS grading system for Grades 0 through 3 (Table 3), which is based solely on FEV1 and/or ccl is a useful surrogate marker for BO: it is easy to measure by standardized spirometry and is reproducible; it becomes abnormal prior to histologic confirmation [Chacon 2000]; and it displays high sensitivity and specificity when assessed against biopsy- and autopsy-confirmed BO [Heng 1998]. In the following Tables, "baseline" is defined as the patient's personal best FEV1 following transplant.

Table 3. Bronchiolitis obliterans syndrome (BOS) classification

Original classification (1993)		2002 Classification		2019 ISHLT Classification	
-	-	BOS 0	$FEV_1 > 90\%$ of baseline and $ > 75\% $ of baseline	-	-
BOS 0	FEV 1 80% or more of baseline	BOS 0-p	FEV 1 81% to 90% of baseline and/or $\leq 75\%$ of baseline	CLAD 0	FEV 1 > 80% of baseline
BOS 1	FEV 1 66% to 80% of baseline	BOS 1	FEV 1 66% to 80% of baseline	CLAD 1	FEV 1 66-80% of baseline
BOS 2	FEV 1 51% to 65% of baseline	BOS 2	FEV 1 51% to 65% of baseline	CLAD 2	FEV 1 51-65% of baseline
BOS 3	FEV 1 50% or less of baseline	BOS 3	FEV 1 50% or less of baseline	CLAD 3	FEV 1 35-50% of baseline
-	-	-	-	CLAD 4	FEV 1 < 35% of baseline

BOS: bronchiolitis obliterans syndrome; CCI ; FEV1: forced expiratory volume in 1 second [Estenne 2002]. CLAD: chronic lung allograft dysfunction.

Table 4. Basic Phenotypes of Chronic Lung Allograft Dysfunction

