#### 10 SELECTION AND WITHDRAWAL OF PATIENTS

#### 10.1 Patient Inclusion Criteria

- 1. Adult patients of  $\geq$  18 years who received a double lung transplant at least 12 months prior to Screening.
- 2. Patients with BOS diagnosis defined as CLAD-BOS phenotype with:
  - a) Screening  $FEV_1$  between 85-51% of personal best  $FEV_1$  value post-transplant. OR
    - b) Screening FEV1 >85% of personal best FEV1 associated with EITHER a  $\geq$  200 mL decrease in FEV1 in the previous 12 months OR according to medical history showing BOS progression.
- 3. Diagnosis of CLAD-BOS must be made at least 12 months after lung transplantation and
  - a) within 12 months prior to the screening visit.

OR

- b) more than 12 months from screening and patient must have shown a decline in FEV1 ≥ 200ml in the previous 12 months before screening, which is not due to acute infection or acute organ rejection.
- 4. Patients in whom the diagnosis of BOS has been confirmed by the elimination of other possible causes of obstructive or restrictive lung disease (CLAD RAS phenotype, see Protocol Specific Definitions).
- 5. Patients should be on a drug maintenance regimen of immunosuppressive agents including tacrolimus, a second agent such as but not limited to MMF or azathioprine, and a systemic corticosteroid such as prednisone as third agent. The regimen must be stable within 4 weeks prior to randomization with respect to the therapeutic agents. In case a patient is also receiving concomitant azithromycin for prophylaxis or treatment of BOS, in addition to the previously described immunosuppressive regimen, azithromycin must be on a stable regimen for at least 4-weeks prior to randomization.
- 6. Patients capable of understanding the purposes and risks of the clinical trial, who have given written informed consent and agree to comply with the clinical trial requirements/visit schedules, and who are capable of aerosol inhalation. Patients must consent to retrieve prespecified data from the historic medical record (e.g., information related to the transplant surgery; spirometry data; medication use).
- 7. Women of childbearing potential must have a negative serum or urine pregnancy test within 7 days prior to randomization and must agree to use one of the methods of contraception listed in Appendix II through their End of Study Visit.
- 8. Patients have no concomitant diagnoses that are considered fatal within one year (12 months) of Screening.

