- **Physical Examination:** Body weight and height, cardiovascular, respiratory, nervous, gastrointestinal, hepatic, renal, dermatological, musculoskeletal, extremities, eyes, ears, nose, and throat, and lymphatic.
- Vital Signs: Blood pressure, heart rate, body temperature, respiratory rate.

- Clinical Laboratory Tests: All parameters listed in Section 13.1.5 of the protocol, to be performed in the local laboratory at the study site.
- Col Patients will be trained by site personnel on the use of this portable spirometer.
- CCI (on CCI ): FEV1, CCI , FVC, CCI ratio

  A spirometry assessment will be performed on CCI as per

  Section 12.1.1.
- Document historical spirometry data from personal best post-transplant prior to Screening, plus
  - Date of personal best FEV1 post-transplant and all lung function values available (FVC [absolute], FEV1 [absolute], occlude [absolute])
  - Dates of meeting BOS 0-p or BOS 1 criteria and all lung function values available (FVC, FEV1, CCI
- **Blood Sampling:** For determination of serum levels of calcineurin inhibitors and mTor inhibitors
- **Dosages of maintenance immunosuppression:** record on the Concomitant Medication eCRF
- Concomitant Medications/Therapies: Name of drug, dosage, duration
- Adverse Events

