### 8.1.1 Baseline Definition

baseline  $FEV_1$ : the  $FEV_1$  value that is the mean of the best  $FEV_1$  obtained with the study spirometer at the Screening Visit and the pre-randomization best  $FEV_1$  obtained at the Baseline Visit (V1) is referred to as "baseline  $FEV_1$ ". If the value at Screening visit is missing, then the baseline  $FEV_1$  will be the pre-randomization value from the Baseline Visit (V1). If the pre-randomization value at Baseline Visit (V1) is missing, then the baseline  $FEV_1$  will be the value from the Screening Visit.

Other oci baseline spirometry values: will be defined similarly as for Baseline FEV1.

baseline  $\overline{FEV_1}$ : will be defined similarly as for  $\overline{CCI}$  baseline  $\overline{FEV_1}$  but using the home spirometer.

Final Version 5.0 Page 17 of 76

Baseline laboratory values: the last measurement obtained prior to or at the Baseline Visit (V1).

Other baseline measurements: unless otherwise specified, baseline refers to measurement obtained at the Baseline Visit (V1).

[figure not shown]

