#### 14.6 SUBGROUP ANALYSES

Analyses of primary endpoints will be performed on the following subgroups of patients:

- Age class (<55 years, ≥55 years),

- Gender (female, male, undifferentiated),
- Region (North America, all other countries together),
- Severity of disease, defined by:
  - % of baseline FEV₁ over personal best FEV₁ post-transplant (baseline FEV₁ >80%,
     >65–80%,
     >50–65%,
     and ≤50% of personal best FEV₁ post-transplant),
  - baseline FEV1 % of predicted (<70%, ≥ 70%),

  - baseline FEV1/FVC ratio (< 0.7, ≥ 0.7),

  - BLAD at baseline (Yes, No);
- Race (American Indian or Alaskan Native, Asian, Black or African American, Native Hawaiian or Other Pacific Islander, White, Other),
- Use of azithromycin at randomization (Yes/No).

Final Version 5.0 Page 59 of 76

Subgroup levels may be pooled to have an adequate number ( $\geq 10$ ) of patients per strata to perform the analysis. Decision on pooling will be taken during the blinded DRM, before data base lock.

Within each subgroup level, descriptive analyses (section 8.1) will be performed on:

- FEV1,
- FEV1/FVC,
- Time to Progression of BOS.

FEV1 and FEV1/FVC change from baseline will be compared using a two-sample t-test (assuming unequal variances) or, if the required assumptions are not met, a two-sample Mann–Whitney U test.

Comparison of time to progression of BOS curves among treatments will be performed with the log-rank test.

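### SAP 11.3 derives BLAD from FEV1 measured after the BOS decline, which makes it a second cut of FEV1 % predicted that mixes best graft function with BOS loss

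*SAP*

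**What the plan says.** - **Definition.** SAP 11.3: "BLAD patients are defined as patients with baseline FEV 1 /predicted FEV1\*100 <80% [10", where [10] is the cited reference. The result goes in the demographic table.
- **Numerator.** SAP 8.1.1 defines baseline FEV1 as the mean of the best value "obtained with the study spirometer at the Screening Visit and the pre-randomization best" value at Visit 1.
- **Entry.** Protocol 10.1, criterion 2a, admits Screening FEV1 "between 85-51% of personal best" FEV1. Criterion 2b admits patients above 85% who have lost at least 200 mL in the previous 12 months or whose history shows BOS progression. Criterion 3 places the BOS diagnosis before Screening.
- **Protocol tables.** For the BOS and CLAD tables in Protocol 6.1, baseline "is defined as the patient's personal best" FEV1 after transplant.
- **Use.** SAP 14.6 lists "BLAD at baseline (Yes, No") under severity of disease. Beside it stand baseline FEV1 as % of personal best, baseline FEV1 % predicted cut at 70%, and FEV1/FVC.
- **Available data.** Protocol 14.2.1: "Document historical spirometry data from personal best post-transplant prior to Screening", with the date of the personal best.

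**The concern.** The label refers to dysfunction of the graft at its baseline, but the numerator is current function in patients selected for having lost function. A graft that reached a normal FEV1 and then developed BOS can be recorded as having baseline dysfunction.

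Two outputs are affected. The demographic table would report a BLAD prevalence that includes BOS loss. A difference in effect between BLAD 'Yes' and 'No' could come from the graft's best function, from BOS loss or from both, and the split could not tell which. Meanwhile the one quantity that isolates best attained function, personal best divided by predicted, is not among the SAP 14.6 subgroups.

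**Working it through.** The documents state no expected BLAD share, so there is no figure of the plan's own to reproduce.

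**1. Decomposition.** Let r = baseline FEV1 / personal best, and B = personal best as % predicted. Holding predicted FEV1 fixed,

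FEV1 % predicted = r × B.

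SAP 14.6 already has r (% of personal best) and r × B (cut at 70%). BLAD is r × B again, cut at 80%. B alone is absent.

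**2. Threshold.** 'No' requires r × B ≥ 80, so B ≥ 80 / r.

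| r | Personal best needed for 'No' (% predicted) |
|---|---|
| 0.95 | 80/0.95 = 84.2 |
| 0.85 | 80/0.85 = 94.1 |
| 0.80 | 80/0.80 = 100.0 |
| 0.65 | 80/0.65 = 123.1 |
| 0.51 | 80/0.51 = 156.9 |

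If baseline FEV1 equals Screening FEV1, every patient in the 80-51% randomization stratum needs a best of at least 100% predicted to be 'No'.

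**3. Example with the SAP's own equation** (Caucasian man, 55 years, 175 cm, same age used throughout for simplicity). Predicted FEV1 = 0.5536 − 0.01303×55 − 0.000172×3025 + 0.00014098×30625 = 3.634 L. Suppose a personal best of 3.5 L: 3.5/3.634 = 96% predicted. At 80% of best, FEV1 is 2.8 L: 2.8/3.634 = 77% predicted. SAP 11.3 labels him BLAD.

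**4. Overlap with the existing subgroup.** Everyone below 70% predicted is BLAD, and everyone not BLAD is at or above 70%. The two splits differ only for patients from 70 to below 80% predicted.

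**5. Illustrative shares.** These rest on assumptions, because the documents give neither B nor the split of r. Assumed: B normal with mean 75-105 and SD 15 or 20, clipped to 35-150; r uniform on 0.81-0.95 in 15%, 30% or 50% of patients and uniform on 0.51-0.80 in the rest; B and r independent; 400,000 draws per cell. N = 169 randomized (SAP 8.2).

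| Mean B | BLAD by SAP rule | 'No' of 169 | B < 80 | BLAD among those with B ≥ 80 |
|---|---|---|---|---|
| 75 | 88-97% | 5-20 | 60-63% | 70-92% |
| 80 | 83-95% | 8-28 | 50% | 67-90% |
| 85 | 78-92% | 13-37 | 37-40% | 63-88% |
| 90 | 72-88% | 20-48 | 25-31% | 59-84% |
| 95 | 65-83% | 28-59 | 16-23% | 55-80% |
| 100 | 57-77% | 38-72 | 9-16% | 50-75% |
| 105 | 49-71% | 50-86 | 5-11% | 45-69% |

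Across the grid, 7-23% of patients fall from 70 to below 80% predicted, so the 70% and 80% splits agree for 78-93%.

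**6. What the variable tracks.** On this grid, FEV1 % predicted correlates 0.63-0.84 with B and 0.52-0.77 with r. If r is instead taken as uniform over 51-85% or over 66-90%, with mean B 85-95 and SD 18, the correlations are 0.79-0.92 with B and 0.38-0.60 with r. It is a mixture of both in every case.

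**The case against.** The strongest reply is that the SAP is consistent with itself. It defines baseline FEV1 once and uses that definition in 11.3. Protocol 6.1 limits the personal-best meaning of baseline to its own tables. SAP 14.6 files BLAD under severity of disease, which suits a measure of current function. The only BLAD definition in the documents is the one in SAP 11.3, and reference [10] cannot be read here. The version history records that the subgroup was added in SAP 4.0 but gives no reason, so its purpose is an inference from the label. Personal best is also a weaker measurement: it comes from site spirometers, as one value or a mean of two by local practice, whereas study spirometry is centrally over-read.

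Much of this stands, and it rules out several stronger readings that a reader might infer:

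- *Nearly everyone will be BLAD and the 'No' group will be tiny.* This is not shown. Criterion 2b admits patients above 85% of best, and the assumed range is 49-97%. Fewer than 10 'No' patients of 169 occurs only at a mean best of 75-80% predicted.
- *BLAD merely repeats the % predicted subgroup.* The two are nested but not identical.
- *Any BLAD difference is really a BOS-severity difference.* The variable also reflects personal best, often more strongly.

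The reply does not remove the redundancy or the mixing, since both follow from the SAP's own definitions. Nor does it explain why a current-function measure carries a label about the graft's baseline when the Protocol's allograft-dysfunction tables take personal best as baseline.

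**Conclusion.** The point holds in a limited form. As defined, BLAD is FEV1 % predicted cut at 80%, nested with the 70% cut already planned, and it combines best attained graft function with BOS loss. That part needs no assumption, and the 94% and 100% thresholds are exact for patients at 85% and 80% of best.

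The shares (49-97% labelled BLAD; 45-92% of those with a best of at least 80% predicted) rest wholly on assumed distributions and show direction and rough size only. Whether reference [10] calls for personal best cannot be settled from these documents.

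The consequence is small: one row of the demographic table and one exploratory subgroup (descriptive statistics, t-test or Mann-Whitney, log-rank). BLAD is not in the primary model or the testing hierarchy. The correction is still worth making because it is cheap and the label invites a wrong interpretation.

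**What to change.** First check reference [10] for which FEV1 its definition uses. Then take one of two courses in SAP 11.3, the demographic table and SAP 14.6:

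- **Preferred, if reference [10] supports it:** define BLAD as personal best post-transplant FEV1 / predicted FEV1 × 100 < 80%, with predicted FEV1 computed at the age on the date of the personal best. Keep current FEV1 % predicted as its own severity subgroup.
- **Otherwise:** keep the derivation, call it baseline FEV1 below 80% predicted, and do not report it as BLAD.

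The cost is a wording change and, for the first course, one derivation from data already collected. The downside of the first course is reliance on site spirometers for the personal best. The existing subgroup by % of personal best already accepts that limitation.

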# 12 Immunosuppressants

Immunosuppressants are collected in the Concomitant Medications CRF form.

As per CRF completion guidelines, immunosuppressants are to be collected using the same measurement unit i.e., mg. In those cases where it is not done, considerations will be taken on ongoing basis (at DRM at the latest) to convert units for each immunosuppressive agent to allow cumulative dose to be calculated. Immunosuppressant medications will be coded using the World Health Organization (WHO-DD) classification system and grouped by drug class and PT.

In order to identify immunosuppressants among concomitant medications, any of the following two rules will be applied.

1. Only the following routes are to be considered: oral, intramuscular, intravenous, and subcutaneous;

the following codes are to be considered:

- o L04A Immunosuppressants:
  - 1. L04AA Selective immunosuppressants,
  - 2. L04AB Tumor necrosis factor alpha (TNF- $\alpha$ ) inhibitors,
  - 3. L04AC Interleukin inhibitors,
  - 4. L04AD Calcineurin inhibitors,
  - 5. L04AX Other immunosuppressants;
- o H02AB Glucocorticoids (all);

Final Version 5.0 Page 35 of 76

L04AD02 Tacrolimus, and route = sublingual.

### 12.1 Basic Immunosuppressants

As per protocol, regardless of treatment assignment, all clinical trial participants must be on a maintenance regimen of immunosuppressive agents including tacrolimus, a second agent such as but not limited to mycophenolate motfetil (MMF) or azathioprine, and a systemic corticosteroid such as prednisone as third agent. At each visit, the average maintenance doses of immunosuppressive agents will be recorded by the Investigator on the Concomitant Medication eCRF.

Basic immunosuppressants refer to maintenance regimen of immunosuppressive agents and include the following:

- Calcineurin inhibitors (Tacrolimus, Cyclosporine A);
- Antimetabolicte (Antimetabolite) agents (MMF, Azathioprine);
- mTOR inhibitor (Everolimus, Sirolimus);
- Selective costimulation blocker (Belatacept);
- Corticosteroids.

The total basic immunosuppression administered from the day of randomization will be evaluated.

Basic immunosuppressives will be coded by Anatomical Therapeutic Code (ATC) codes, and will be summarized by treatment group for SAF, FAS and PPS.

A p-value will be obtained from the Fisher's Exact test for the comparison of patients with any basic immunosuppressants from L-CsA plus SoC versus patients with any basic immunosuppressants from SoC alone, for each class of basic immunosuppressants listed above.

Descriptive statistics on cumulative doses for basic immunosuppressants will be provided:

- for the whole treatment period (from day of randomization to end of study),
- for each period between study visits (V1 to V2, V2 to V3, etc.),
- cumulatively for each period between study visits (V1 to V2, V1 to V3, V1 to V4, etc.),

where periods between study visits  $V_i$  to  $V_{i+1}$  (with i=2,3,4, etc) is defined as the interval starting from the first day post visit  $V_i$  and ending the last day of visit  $V_{i+1}$  (included). For V1 to V2 the date of V1 must be considered too.

Final Version 5.0 Page 36 of 76

Descriptive statistics will be calculated for each class of basic immunosuppressants listed above and overall. If a patient took more than one basic immunosuppressant related to the same class, then the total dose will be taken into consideration in the calculation.

P-values will be obtained from the Fisher's Exact test for the comparison of patients with any basic immunosuppressants, including each of basic immunosuppressant listed above from L-CsA plus SoC versus patients with any basic immunosuppressants from SoC alone at each time interval (V1 to V2, V1 to V3, ...., V1 to V9).

Exposure to immunosuppressant medication details will be summarized similarly for each category of basic immunosuppressant, and overall for all.

This includes the calculation of the duration of intake (date of last basic immunosuppressant intake - date of first basic immunosuppressant intake + 1). The duration will be calculated by summing the duration of the associated treatments. The overlapping days will be counted only once.

The ratio between the cumulative dose and intake duration will be used to produce the dose per day. The overall dose per day per patient will then be displayed for each treatment group for each time interval along with the 95% confidence interval.

By-patient listings will be provided for all basic immunosuppressants for FAS.

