#### 9.2 Trial Design

This is a Phase III, prospective, multi-center, randomized, controlled clinical trial in the treatment of BOS in adult recipients of a bilateral pulmonary allograft. Approximately 160-170 patients are planned for enrollment. The clinical trial will be conducted in approximately 43 centers worldwide. Patients will be randomly allocated to receive either L-CsA plus SoC or SoC alone for the treatment of BOS. Patients will be monitored every 4-8 weeks over 48 weeks for efficacy parameters and for all safety evaluations.

The rationale for not using a placebo control is driven by concerns that a sucrose-containing formulation could increase a potential risk of pulmonary infection without the benefit of L-CsA. Sucrose is a lyoprotectant in the manufacturing process. After carefully weighing alternative options for lyoprotection, no sugar-free alternatives that qualify as real placebo (i.e., undistinguishable by means of appearance, taste or smell) could be identified. Therefore, a randomized controlled trial versus SoC is the only suitable alternative.

An open-label clinical trial generally bears the potential regarding biased patient treatment and care, and thus trial outcome. However, for this trial the risk of bias is considered low because of the following reasons:

- Currently, the general strategy to treat BOS is augmentation of immunosuppressive therapy
  to the highest tolerable level unless limited by systemic toxicity. Since application of L-CsA
  via inhalation has not shown to lead to an additional systemic drug burden, dose reductions or
  adaptations of other components of the immunosuppressive cocktail will not be required and
  are not desired.
- Furthermore, the selected primary endpoint FEV1 is an objective parameter and its measurement will be performed according to recommended guidelines of ATS/ERS which have to be respected by each participating center. Following this methodology, a subjective and intentional manipulation of outcome is highly unlikely even if health care professional and patient are aware of the treatment allocation.
- The pulmonary function technicians, respiratory therapists, or physiotherapists who perform spirometry at each site will be blinded to each study patient's study treatment assignment.

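### SAP 12.1: the Fisher tests on any use of calcineurin inhibitors, corticosteroids and any basic immunosuppressant sit at the ceiling by eligibility, so their p-values cannot reflect escalation after randomization

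*SAP*

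**What the plan says.** SAP 12.1 lists five classes of basic immunosuppressant: calcineurin inhibitors, antimetabolites, mTOR inhibitors, belatacept and corticosteroids. It plans Fisher's exact tests on the number of patients with any use: "A p-value will be obtained from the Fisher's Exact test for the comparison of patients with any basic immunosuppressants from L-CsA plus SoC". The comparator is the SoC-alone arm, and one such test is planned per listed class. The comparison is repeated, overall and by listed agent, "at each time interval (V1 to V2, V1 to V3, ...., V1 to V9"). The first interval includes the V1 date itself, so every cumulative interval contains the regimen in use at randomization.

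The same section says that "all clinical trial participants must be on a maintenance regimen of immunosuppressive agents including tacrolimus", together with a second agent and a systemic corticosteroid. Criterion 5 in Protocol 10.1 describes the regimen as "including tacrolimus, a second agent such as but not limited to MMF or azathioprine, and a systemic corticosteroid such as prednisone as third agent" and asks that it be stable in the four weeks before randomization.

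SAP 12.1 also plans descriptive cumulative doses by class and interval, and dose per day by arm with a 95% confidence interval. SAP 12.2 counts other immunosuppressants by ATC code and states no test.

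**The concern.** The trial is open-label. Treating physicians know the arm, and the protocol synopsis leaves changes to standard of care to the investigator's discretion. Protocol 9.2 says: "Currently, the general strategy to treat BOS is augmentation of immunosuppressive therapy" to the highest tolerable level. It then argues that bias is low, partly because the other components of the regimen should not need adapting when L-CsA is added. FEV1 measured after augmentation stays in the primary analysis (SAP 14.1.1). Whether background immunosuppression was escalated unequally therefore matters when the treatment difference is interpreted.

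The Fisher tests are the only tests of background immunosuppression in SAP 12. If a count is fixed by eligibility before the first randomized day, its p-value describes the entry criterion and not what happened afterwards. A row of values near 1.0 could then be taken for evidence of balance.

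**Working it through.** The plan states no power or expected count for these tests, so there is no plan figure to reproduce.

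**Inputs.** SAP 8.2 gives 169 randomized patients. Allocation is 1:1 (Protocol 9.3). The actual split is not given, so I assume 84 L-CsA and 85 SoC. Tests are taken as two-sided at 0.05, which SAP 12.1 does not specify. Baseline use and the rate of new starts are assumptions, shown over a range.

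**Step 1: which classes does criterion 5 fix?**
- Calcineurin inhibitors: fixed, because tacrolimus is named. A post-randomization exchange of tacrolimus for systemic cyclosporine A (allowed in Protocol 11.3.4) stays in the class. A move to an mTOR inhibitor (Protocol 11.3.1) leaves the patient counted as a user, because every interval includes V1.
- Corticosteroids: fixed.
- Any basic immunosuppressant: fixed as a consequence.
- Antimetabolites: probably high but not fixed, because the second agent is left open.
- mTOR inhibitors and belatacept: not required at entry.

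**Step 2: Fisher p at the ceiling.**
- 84/84 vs 85/85: p = 1.00.
- 82/84 vs 85/85: both non-users fall in the 84-patient arm with probability (84 × 83)/(169 × 168) = 6,972/28,392 = 0.25. The opposite extreme has probability (85 × 84)/28,392 = 0.2515, which is larger and is not counted. So p = 0.25.
- With 85/85 in one arm, 80/84 in the other gives p = 0.059 and 79/84 gives p = 0.029. Five or six patients of one arm would have to lack a drug class that entry requires before p came near 0.05. That would signal eligibility deviations, not augmentation.

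**Step 3: response to unequal escalation.** Let b be the proportion already using the class at V1 in each arm, and s the proportion of non-users who start it later. Any-use prevalence is b + (1 − b)s. Take s = 10% on L-CsA and 30% on SoC. Rejection rates are summed exactly over the two binomial distributions.

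| b | L-CsA any use | SoC any use | Any-use test rejects |
|---|---|---|---|
| 0% | 10.0% | 30.0% | 89% |
| 5% | 14.5% | 33.5% | 80% |
| 10% | 19.0% | 37.0% | 71% |
| 20% | 28.0% | 44.0% | 54% |
| 85% | 86.5% | 89.5% | 8.4% |
| 90% | 91.0% | 93.0% | 6.6% |
| 95% | 95.5% | 96.5% | 3.5% |
| 100% | 100% | 100% | 0% |

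**Step 4: the same test on post-randomization change.** If 10% and 30% of patients have a start or a dose increase, Fisher's test on that flag rejects in 89% of trials, whatever the baseline use. Other assumed rates give 69% (10% vs 25%), 83% (15% vs 35%) and 38% (10% vs 20%).

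For an mTOR-type class, counting only new starters over all patients means comparing (1 − b) × 10% with (1 − b) × 30%. This rejects in 84% at b = 10% (9% vs 27%) and 78% at b = 20% (8% vs 24%), against 71% and 54% for any use. So part of the fall in Step 3 comes from having fewer non-users, and the larger part from mixing in baseline users.

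Giving the 85 patients to L-CsA and 84 to SoC moves these rates by at most about five percentage points (89% becomes 91%) and leaves the 0% unchanged.

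**The case against.** The strongest counter-argument is that the tests as a set are not blind. An mTOR inhibitor is the fourth drug that Protocol 11.3.1 names and its alternative to a calcineurin inhibitor, and the mTOR test can detect unequal starts: 4/85 vs 12/84 gives p = 0.038. A reader might infer that all five classes are at the ceiling, so that no test in SAP 12.1 could show an imbalance. Criterion 5 does not support that reading. Even for the fixed classes, about 100% is expected but not guaranteed: the protocol says patients should be on the regimen, while the SAP says they must be.

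A reader might also infer that augmentation is tested nowhere. That cannot be said either. SAP 14.3.5 plans a while-on-treatment analysis that treats initiation of additional immunosuppression as an intercurrent event, with time-to-initiation summaries. It refers to section 14.5.1 for details of those therapies. That section is redacted, and the version 5.0 history entry shows that it contains a logistic regression or an exact test. A related between-arm comparison may already exist there. The dose outputs in SAP 12.1 could also show differences, though only descriptively, and they do not count patients escalated.

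Finally, no text says that a large p will be read as balance, and these tests are not in the visible part of the testing hierarchy in SAP 8.4.

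All of this limits the point. None of it makes the calcineurin inhibitor, corticosteroid and overall p-values informative.

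**Conclusion.** The point holds for three comparisons: calcineurin inhibitors, corticosteroids and any basic immunosuppressant. There p is about 1 by construction, and no dose increase or within-class switch after randomization can move it. The antimetabolite test is probably nearly as insensitive (rejection of 3.5% to 8.4% at an assumed 95% to 85% entry use), but the documents do not fix that prevalence. The mTOR inhibitor and belatacept tests work with reduced power, falling from 89% with no baseline users to 71% at 10% and 54% at 20%.

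These rates rest on the assumed 84/85 split and on assumed starts of 10% versus 30%. The ceiling itself rests only on the eligibility rule and on intervals that begin at V1. The primary test is unaffected. What is at stake is whether the background-therapy tables can support the low-bias argument of an open-label trial. The change is worth making because it is cheap and turns uninformative tests into informative ones.

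**What to change.** In SAP 12.1, change the Fisher numerator to patients with a basic immunosuppressant started after the randomization date that was not in use at randomization, or with a dose increase over the randomization dose of the same agent. Apply it per class and overall, for the same V1-to-Vk intervals. Beside each p-value, report the between-arm risk difference with its 95% CI.

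Report stops and dose reductions as a separate count, because the argument in Protocol 9.2 concerns reductions and adaptations as well as additions. Keep the any-use counts as description without p-values. State that a non-significant p is not to be read as balance. Align the flag with the definition of additional immunosuppressive therapy in SAP 14.5.1, so that the two do not conflict or duplicate each other.

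The cost is a wording change and one derived flag. Doses and start, stop and change dates are already recorded in the eCRF (Protocol 11.3.1). The downside is some programming, and some dose changes made only to reach a trough level will be counted as increases.
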